1.5.2 Potential Benefits

Animals that received VIS410 as either treatment or prophylaxis experienced prolonged survival compared with vehicle/placebo-treated animals following challenge with various strains of influenza A virus. The Phase 2a challenge study demonstrated a statistically significant reduction in viral AUC following treatment with VIS410 compared with placebo (Section 1.3).

At this time, the actual benefits of VIS410 for the treatment of influenza patients are unknown. However, data from a recently conducted human challenge study in 31 healthy volunteers given influenza A demonstrated a statistically significant decrease in shedding of influenza virus with a shorter duration of symptoms (2 days) in the VIS410-treated group compared with the placebo group.

2. STUDY OBJECTIVES

2.1 PRIMARY OBJECTIVE

- Assess the safety and tolerability of a single intravenous (IV) dose of VIS410 in patients with uncomplicated influenza infection

2.2 SECONDARY OBJECTIVES

- Evaluate the efficacy of VIS410 compared with placebo on the time to alleviation of clinical symptoms of acute uncomplicated influenza
- Evaluate the effect of VIS410 on severity of influenza infection
- Assess the pharmacokinetics of VIS410 in serum
- Assess the effects of VIS410 on viral shedding
- Assess the immunogenicity of VIS410

2.3 EXPLORATORY OBJECTIVES

- Assess the pharmacokinetics of VIS410 from nasopharyngeal secretions
- Assess viral isolates to determine the emergence of VIS410-resistant viruses
- Assess correlations between virology, safety, pharmacokinetics, viral shedding, clinical symptoms, and other endpoints
- Assess the anti-influenza immune response

3. STUDY ENDPOINTS

3.1 PRIMARY ENDPOINTS

- The proportion of subjects with adverse events (AEs) and serious adverse events (SAEs) following administration of VIS410
- The proportion of subjects with treatment-emergent AEs (TEAEs) including hypersensitivity reaction, anaphylactic reaction, and AEs of special interest (AESIs) following dosing

3.2 SECONDARY ENDPOINTS

- The incidence, severity, and duration of signs and symptoms of influenza-like illness as assessed by the Influenza Patient Reported Outcomes questionnaire after a single IV dose of VIS410
- Percentage of participants requiring hospitalization for influenza-related complications
- Duration of hospitalization for influenza-related complications
- Percentage of participants with complications of influenza
- Percentage of participants with influenza A relapse/reinfection
- VIS410 PK parameters (C_{max} , t_{max} , $AUC_{0-\infty}$, AUC_{0-last} , $t_{1/2}$, V_d , CL) in serum
- The difference between VIS410 and placebo treatment groups in viral AUC from nasopharyngeal swabs
- The difference between VIS410 and placebo treatment groups in peak viral load and time to resolution of viral load from nasopharyngeal swabs
- Titer of anti-VIS410 antibody-positive samples

3.3 EXPLORATORY ENDPOINTS

- PK parameters (C_{max} , t_{max} , $AUC_{0-\infty}$, AUC_{0-last} , $t_{1/2}$) of VIS410 from nasopharyngeal secretions
- Genotypic and phenotypic assessment to determine the emergence of VIS410-resistant viruses
- Correlations between serum and/or nasopharyngeal PK with viral load, clinical symptoms, presence of ADAs, and additional endpoints
- Titer of anti-influenza A antibodies by hemagglutinin inhibition assay (HAI) in serum
- Correlations between virology and safety parameters and/or additional parameters may be explored

4. STUDY DESIGN

4.1 OVERVIEW OF STUDY DESIGN

This is a Phase 2a randomized, double-blind, placebo-controlled study to be conducted in approximately 150 subjects with uncomplicated influenza. This study will include approximately 50–75 clinical sites worldwide.

Subjects will be admitted to an infusion unit for drug administration and observation following infusion. The study is designed to compare an infusion of a single high or low IV

[figure not shown]
dose of VIS410 against placebo. Subjects will be assigned randomly to receive VIS410 at a dose of 2000 mg (low dose) or 4000 mg (high dose) or placebo (0.9% sodium chloride) at a ratio of 1:1:1 using a permuted block randomization method. Eligible subjects will receive VIS410 2000 mg, VIS410 4000 mg, or placebo administered as a single IV infusion over 2 hours on Day 1. Subjects will receive a pretreatment regimen of diphenhydramine 50 mg PO and ibuprofen 400 mg PO or acetylsalicylic acid 325 mg PO 60 minutes before infusion.

The subjects will be observed for at least 2 hours after the end of the infusion and will have a follow-up phone call in the evening of the dosing day to ensure subjects' safety and well-being. Subjects will return for follow-up visits on Days 3 (± 1 day), 5 (± 1 day), 7 (± 1 day), 14 (± 3 days), 28 (± 3 days), 56 (± 7 days) and 100 (± 7 days). In addition, between clinic visits up to Day 7 (e.g., Days 2, 4 and 6) subjects will receive a follow-up telephone call to ensure compliance with FluPRO Influenza Symptom Questionnaire and review any new or worsening signs or symptoms. The Schedule of Assessments is presented in Table 1.

An independent Data Safety Monitoring Board (DSMB) will be established to review all available safety data after 30 subjects have completed the Day 5 visit and again after 75 subjects have completed the Day 28 visit. In addition, following the first DSMB, the DSMB will convene if the overall relative GI adverse event rate reaches 50% or the rate of moderate GI adverse events reaches 25%.

A schematic overview of the study design is shown in Figure 1. The assessments performed are summarized per visit in the Time and Events Schedule.

Figure 1. Schematic Overview of the Study

4.2 DISCUSSION OF STUDY DESIGN

Dose Selection

Various methods were utilized to determine the efficacious dose of VIS410 in humans for the treatment of influenza. These methods included evaluation of doses and exposures to provide VIS410 levels which exceed in vitro susceptibility measures, including neutralization EC_{50} and binding affinity, bridging efficacious doses in preclinical species to humans based on a mg/kg dose and PK, and exploratory PK/PD analyses of serum and nasal exposure versus antiviral activity of VIS410 in a human influenza virus challenge study. VIS410 broadly

neutralizes influenza A strains in vitro with EC₅₀ values ranging from 0.03 to 64.2 µg/mL (median of 3.15 µg/mL) and binds with high avidity (30 to 380 picomolar) to HA across Group 1 and Group 2 subtypes. VIS410 doses of approximately 2300 mg will result in C_{max} serum level of 873 µg/mL, which is well above median EC₅₀ of 3.15 µg/mL in serum and nasal cavity for the duration of viral shedding. Furthermore, in preclinical animal studies, VIS410 demonstrated efficacy at doses of 20 to 30 mg/kg or less against various Group 1 and Group 2 influenza A strains with EC₅₀ values ranging from 0.57 to 2.4 µg/mL. Using a standard mg/kg conversion, these doses equate to 1500–2300 mg dose in humans (assuming a 75-kg subject). In a human influenza virus challenge study a single dose of 2300 mg demonstrated significant reduction in viral load area under the curve (AUC) and peak viral load compared with placebo, suggesting that doses of approximately 2300 mg may be efficacious in naturally occurring influenza infection. For strains with higher EC₅₀, doses greater than 2300 mg may be necessary to achieve adequate concentration at the primary site of infection. Based on these data, doses of 2000 and 4000 mg were selected for evaluation in this Phase 2a study. A dose of 4000 mg will ensure separation in VIS410 systemic exposures from the 2000 mg dose level to identify potential differences in safety and efficacy between the 2 doses. A dose level of 2000 mg provides a safety margin of approximately 9.4-fold to the nonclinical NOAEL (250 mg/kg), with the 4000 mg dose providing a safety margin of approximately 4.7-fold, assuming a 75-kg subject. In addition, in the Phase 1 pretreatment study (VIS410-102) doses of 2300 and 3800 mg were well tolerated following a pretreatment regimen of diphenhydramine plus ibuprofen.

Selection of Study Population

Approximately one hundred fifty (150) subjects will be enrolled in 3 equal arms: VIS410 2000 mg, VIS410 4000 mg, and placebo. The subjects will be carefully screened for eligibility.

4.3 INCLUSION CRITERIA

Subjects meeting all of the following criteria are eligible to participate in this study:

- 1) Male and female subjects aged ≥18 years and <65 years
- 2) Women should fulfill one of the following criteria:
 - a) Post-menopausal; either amenorrhea ≥12 months or follicle stimulating hormone >40 mIU/mL as documented in their medical history.
 - b) Surgically sterile; hysterectomy, bilateral oophorectomy, or tubal ligation.
 - c) Women of childbearing potential participating in heterosexual sexual relations must be willing to use adequate contraception from screening until 60 days post-infusion, per Section 7.1.2.
- 3) Non-vasectomized (or vasectomized less than 6 months prior to dosing) male subjects who have a female partner of childbearing potential must use an effective birth control method (see Section 7.1.2) when having heterosexual intercourse, from screening until 60 days post-infusion.
- 4) Test positive for influenza A by Rapid Antigen Test performed with a commercially available test on an adequate nasopharyngeal specimen in accordance with the manufacturer's instructions

- 5) Presence of at least one respiratory symptom (cough, sore throat, or nasal symptoms) of moderate to severe intensity, or presence of at least one constitutional symptom (myalgia [aches and pains], headache, feverishness, or fatigue) of moderate to severe intensity
- 6) Onset of symptoms (time when the temperature was first measured as elevated [temperature of $\geq 100.4^{\circ}\text{F}$ or $\geq 38^{\circ}\text{C}$], OR the time when the subject experienced at least one respiratory symptom or at least one constitutional symptom) no more than 72 hours before the start of infusion
- 7) Subject is able and willing to comply with study procedures, as per protocol
- 8) Subject is able and willing to give voluntary written informed consent

4.4 EXCLUSION CRITERIA

Subjects meeting any of the following criteria are excluded from participation in this study:

- 1) Use of NSAIDs or antihistamines within 6 hours of study drug dosing with the exception of those used as part of the pretreatment regimen.
- 2) History of intolerance or allergic response to monoclonal antibodies and/or pretreatment medications (diphenhydramine, ibuprofen and acetylsalicylic acid)
- 3) History of receiving monoclonal antibody products within 3 months prior to enrollment in this study or planned administration during the study period
- 4) Subjects in whom nasopharyngeal swabbing is not possible
- 5) Subject weight less than ($<$) 45 kg
- 6) Subjects with clinical history that would lead to increased risk of influenza complications including but not limited to clinically significant cardiac disease, moderate to severe asthma, or other moderate to severe chronic obstructive pulmonary disease, metabolic syndrome including moderate to severe diabetes or active tuberculosis.
- 7) History of chronic GI disease, including bleeding, ulceration, Irritable Bowel Syndrome, systemic mastocytosis, or chronic diarrhea
- 8) Women who are pregnant, breast-feeding, or considering becoming pregnant.
- 9) Patients with hypoxemia requiring oxygen support.
- 10) Clinical evidence of worsening of any chronic medical condition (temporally associated with the onset of symptoms of influenza) which, in the Investigator's opinion, indicates that such finding(s) could represent complications of influenza
- 11) Presence of immunocompromised status due to chronic illness, previous organ transplant, or use of immunosuppressive medical therapy including systemic steroids.
- 12) Presence of known human immunodeficiency virus (HIV) infection PLUS any one of the following:
 - a) A CD4 count ≤ 500 cells/mm³ (CD4 count obtained within the 3 months prior to screening)
 - b) An Acquired Immune Deficiency Syndrome-defining illness. (HIV testing required at screening visit for all patients with no documented HIV status within 3 months prior to screening.)
- 13) Presence of known chronic hepatitis B or hepatitis C.
- 14) Receipt of any dose of antiviral therapy such as, but not limited to, rimantadine, amantadine, peramivir, zanamivir, laninamivir or oseltamivir in the 7 days prior to screening

- 15) Enrollment in any other investigational drug or device study, any disease or vaccine study within 30 days prior to Day 1 or within 5 half-lives of the investigational compound, whichever is longer
- 16) Presence of any pre-existing illness that, in the opinion of the Investigator, would place the subject at an unreasonably increased risk through participation in this study
- 17) Subjects unable to comply with study protocol procedures and study visit schedules for whatever reason
- 18) Subjects unable to take oral predose medication
- 19) Known or suspected alcohol or drug abuse, that is, abuse of a level that would compromise the safety or cooperation of the subject in the opinion of the Investigator
- 20) Subjects on chronic medications where the dose has not been stable for at least 3 months

5. TREATMENT(S)

Manufacturing, packaging, and labelling of the investigational product, VIS410, is done under the responsibility of the Sponsor.

5.1 PHYSICAL DESCRIPTION OF THE STUDY DRUG

The investigational product is manufactured by KBI Biopharma and Lyophilization Services of New England in accordance with Good Manufacturing Practice as required by the current Good Clinical Practice (GCP).

VIS410 is colorless to slightly yellow, clear to opalescent solution; essentially free of particles. VIS410 is formulated at a concentration of 25 mg/mL in 40 mM citrate-sodium phosphate, 150 mM sodium chloride, and 0.025% polysorbate 80.

The investigational product will be provided by the Sponsor. VIS410 will be supplied in Type I 20-mL glass vials containing a nominal 20 mL solution. A copy of the certificate of analysis of the investigational product will accompany the study drug to the clinical center.

The study drug will be labelled according to local law and regulatory requirements.

Specific dilution procedures of the study drug will be described in detail in the dispensing protocol.

Placebo will be a normal saline solution (0.9%) and will be prepared by the pharmacist.

5.2 OTHER MEDICATION ADMINISTERED IN THE STUDY

Chronic medications not listed in excluded concomitant medications, are permitted where the dose has been stable for at least 3 months prior to screening.

In case of hospitalization due to worsening of influenza symptoms, subjects should be managed per standard of care and local guidelines, which may include use of neuraminidase inhibitors.

Subjects will receive a pretreatment regimen of diphenhydramine 50 mg PO and either ibuprofen 400 mg PO or acetylsalicylic acid 325 mg PO 60 minutes before infusion. If the subject has any history of delayed gastric emptying, including premenstruation syndrome or menstruation, the subject may receive premedications 120 minutes prior to IV infusion.

5.3 STORAGE AND DRUG ACCOUNTABILITY

5.3.1 *Study Drug*

The Investigator (or designee) is responsible for the safe storage of all study drugs assigned to the clinical site. The investigational product should be stored in a locked, secure storage facility with access limited to those individuals authorized to dispense the investigational product, and maintained within the appropriate ranges of temperature. All study drugs must be stored in the original packaging and as specified at delivery.

The study investigational product be stored between 2°C and 8°C and should be protected from light during storage at the clinical site.

Regular temperature recordings of the study drug storage refrigerator at the clinical site should be performed. In case a deviation in the storage conditions should occur, the site must not further dispense the affected study drug; instead, the Sponsor should be notified and will confirm whether or not the study drug may be further dispensed.

The Investigator is responsible for ensuring that all study drugs received at the clinical site are inventoried and accounted for throughout the study.

Study drugs should be dispensed under the supervision of the Investigator, a qualified member of the investigational staff, or by a hospital/clinic pharmacist. The Investigator must maintain accurate records demonstrating date and amount of drugs administered to whom and by whom. Study drugs will be supplied only to subjects participating in the study.

The Monitor responsible for drug accountability will periodically check the supplies of study drugs held by the Investigator or pharmacist to ensure accountability and appropriate storage conditions for all the study drugs held at the site.

Unused study drugs must be available for verification by the Sponsor's Monitor responsible for drug accountability during on-site monitoring visits. Any discrepancies between returned and expected returned study drugs should be explained.

After the last visit of the last subject in the study (LSLV), any used and unused investigational product will be returned to the Sponsor, or destroyed with the Sponsor's written permission (in this case a certificate of destruction will be provided and filed in the Trial Master File).

Hazardous materials such as used needles and syringes should be disposed of immediately in a safe manner and therefore will not be retained for drug accountability purposes.

5.4 DOSE AND ADMINISTRATION

The site's unblinded pharmacist or properly trained designee will prepare the VIS410 or placebo according to the instructions in the pharmacy manual. The required amount of VIS410 to be dosed (2000 mg or 4000 mg) will be diluted with normal saline up to a total volume of 200 mL. For placebo subjects, 200 mL of normal saline will be prepared.

The study infusion will be administered IV using a 0.22 µm in-line filter and will be controlled by a volumetric pump. Standard, uniform-length infusion lines will be used and

microfilters will be provided by the Sponsor. Length of IV line will be set for maximum volume of 25 mL. The infusion bag will be covered with an opaque sleeve in the pharmacy to maintain the study blind. The product will be administered IV at a rate of 100 mL/h, over 2 hours. After 200 mL of the diluted dose has been administered (the infusion bag is empty), the infusion line will be flushed with 25 mL of normal saline to ensure the total product dose is delivered. The infusion time may be longer at the Investigator's discretion based on local infusion site-related symptoms up to a maximum of 4 hours. VIS410 or placebo will be administered within 48 hours of being prepared by the study pharmacist. All doses of study drug will be administered in the clinic under the direct supervision of the Investigator or designee. Following administration, subjects will be observed for at least 2 hours at the infusion center and discharged if considered safe by the investigator. Prior to discharge, all subjects will be counseled on the potential GI AEs and management of these events.

Pretreatment: Subjects will be given a pretreatment regimen of diphenhydramine 50 mg PO with ibuprofen 400 mg PO or acetylsalicylic acid 325 mg PO 60 minutes before the IV infusion. If the subject has any history of delayed gastric emptying, including premenstruation syndrome or menstruation, they may receive premedications 120 minutes prior to IV infusion. In subjects with underlying renal impairment, caution should be taken with use of NSAIDs (ibuprofen or acetylsalicylic acid). Subjects with renal impairment must be adequately hydrated prior to administration of the pretreatment regimen and renal function should be monitored to ensure subject safety.

5.5 TREATMENT COMPLIANCE

To ensure treatment compliance, all study drug infusions will be supervised by the Investigator or his/her designee.

5.6 DATA SAFETY MONITORING BOARD

An independent DSMB will be established to review all available safety data after 30 subjects have completed the Day 5 visit and again after 75 subjects have completed the Day 28 visit. In addition, following the first DSMB, the DSMB will convene if the overall relative GI adverse event rate reaches 50% or the rate of moderate GI adverse events reaches 25%. Study enrollment and dosing will continue whilst the DSMB evaluates data.

Assessment of subject safety will be determined from vital sign measurements ECGs, physical examinations, hematology, chemistry and urinalysis laboratory testing, use of concomitant medications, and review of AEs should they occur.

If requested by the DSMB, additional meetings can be scheduled to follow up further safety data during the study. The DSMB will review the safety data in detail. If any safety concern is raised by the DSMB, treatment can be temporarily or permanently halted.

Doses may be adjusted downward at the discretion of the DSMB based on review of safety data including GI adverse events. Further details will be described in a separate DSMB charter.

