
call in the evening of the dosing day to ensure subjects' safety and well-being. Subjects will return for follow-up visits on Days 3 (± 1 day), 5 (± 1 day), 7 (± 1 day), 14 (± 3 days), 28 (± 3 days), 56 (± 7 days) and 100 (± 7 days). In addition, between clinic visits up to Day 7 (e.g., on Days 2, 4 and 6) subjects will receive a follow-up telephone call to ensure compliance with FluPRO Influenza Symptom Questionnaire and review any new or worsening signs or symptoms.
 
The Schedule of Assessments is presented in Table 1.
 
In case of clinical worsening of influenza-related symptoms recorded at baseline or development of two new symptoms after 48 hours of study drug administration, additional antiviral prescription medication may be used, at the discretion of the Investigator, for management of influenza-like symptoms per standard of care. The use of over-the-counter, symptom-modifying drugs such as non-steroidal anti-inflammatory drugs (NSAIDs), antihistamines, or pseudoephedrine are discouraged and paracetamol/acetaminophen should be encouraged as a replacement medication.
 
In case of hospitalization due to worsening of influenza symptoms, subjects should be managed per standard of care and local guidelines, which may include use of neuraminidase inhibitors. An independent Data Safety Monitoring Board (DSMB) will be established to review all available safety data after 30 subjects have completed the Day 5 visit and again after 75 subjects have completed the Day 28 visit. In addition, following the first DSMB, the DSMB will convene if the overall relative gastrointestinal (GI) adverse event rate reaches 50% or the rate of moderate GI adverse events reaches 25%. Study enrollment and dosing will continue whilst the DSMB evaluates data.
 
Based upon any safety assessments and after mutual agreement with the Investigator (or designee) and the Sponsor, the study may be temporarily or permanently halted.
 
Dosing will temporarily pause whilst the DSMB meets if:
 
 • a drug-related or unexpected drug-related SAE occurs in at least 1 subject • 25% or more subjects have GI symptoms of Grade 3 following the first DSMB. 
Doses may be adjusted downward at the discretion of the DSMB based on review of safety data including GI adverse events.
		

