In the first cohort, 7 subjects received 2300 mg of VIS410 while 5 subjects received placebo. Moderate to severe cramping, loose stool and/or diarrhea were reported in 6 of the 7 subjects receiving VIS410 and none of the placebo subjects. Most symptoms were observed either during the infusion or within 30 minutes of the end of infusion and resolved within ~12 hours. Given the association with infusion, these AEs were all considered possibly related to the study drug. In subsequent cohorts, the addition of a pretreatment regimen containing diphenhydramine mitigated the GI AEs and VIS410 was generally well tolerated with a reduction in frequency and the severity of GI events from moderate/severe to mild.

As statistically significant efficacy was demonstrated with the 2300 mg dose in the first 3 cohorts, the protocol was amended to optimize the tolerability of VIS410. This was done by testing different pretreatment regimens and escalating the dose of VIS410 to 4600 mg in the context of the virus challenge model. This portion of the study (designated as Part 2) was open label; however, virological data were collected to understand viral response and pharmacokinetics/pharmacodynamics.

Eleven subjects were enrolled in Cohort 4 and were inoculated with H1N1 influenza virus and administered VIS410 2300 mg 24 hours later. Four subjects were pretreated with diphenhydramine 50 mg PO and montelukast 10 mg PO (Group 1); 4 subjects were pretreated with diphenhydramine 50 mg PO and ibuprofen 600 mg PO (Group 2); and 3 subjects were pretreated with diphenhydramine 50 mg IV and montelukast 10 mg PO (Group 3).

Three subjects in Groups 1 and 3 subjects in Group 3 experienced transient loose stool that resolved spontaneously. Only 1 of 4 subjects in Group 2 pretreated with diphenhydramine and ibuprofen experienced mild and transient loose stools. Based on these results it was determined that the regimen of diphenhydramine plus ibuprofen resulted in the best tolerability profile and this pretreatment regimen was further assessed in 4 subjects at the

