To date there have been no reports of SAEs. One subject at the 3800 mg dose discontinued study drug infusion due to AEs of nausea, vomiting, chills, and hot flashes. All events resolved after study drug discontinuation despite slow decrease in serum concentration of VIS410. VIS410 was not associated with any signs or symptoms that are consistent with systemic allergic reactions or anaphylaxis. Gastrointestinal events were observed at a higher frequency in the VIS410 treated subjects compared to Placebo. Based on the data from the 2300 mg and 3800 mg dose groups, VIS410 was associated with GI events ranging from mild to severe; however, a 2300 mg dose of VIS410 with a single-dose pretreatment regimen of diphenhydramine and low dose ibuprofen or acetylsalicylic acid was associated with a low rate of GI events (16.7% and 9.1%, respectively). Overall, the most commonly reported events were loose stool, diarrhea, and abdominal cramping. Subjects who received no pretreatment regimen had the highest number of GI AEs ranging from mild to severe. The prolonged infusion of VIS410 (over 4 hours) resulted in a larger number of GI events than the 2-hour infusion (41 events in 10 subjects vs. 18 events in 6 subjects, respectively), suggesting that GI events will not be mitigated by slowing the infusion rate. Pretreatment regimens of an antihistamine (cetirizine) or an antihistamine (diphenhydramine) plus a prostaglandin inhibitor (ibuprofen or acetylsalicylic acid) mitigated the GI events compared with the no pretreatment cohorts. The rate (13 GI events in 7 subjects) and severity of events (12/13 mild) were slightly lower in the cetirizine group than the no pretreatment groups. The lowest rate of GI events with VIS410 was observed in subjects who received the diphenhydramine plus acetylsalicylic acid pretreatment regimen, with only 1 subject reporting a mild episode of loose stool and abdominal pain approximately 22 hours after initiation of study drug administration that resolved spontaneously with no intervention. Another effective pretreatment regimen included diphenhydramine plus ibuprofen at both 2300 and 3800 mg

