8.3 STOPPING RULES OR DISCONTINUATION CRITERIA

The study will be overseen by a DSMB (see Section 5.6). Based upon any safety assessments and after mutual agreement with the Investigator (or designee) and the Sponsor, the study may be temporarily or permanently halted. Study enrollment and dosing will continue whilst the DSMB evaluates data.

Dosing will temporarily pause whilst the DSMB meets if:

- a drug-related or unexpected drug-related SAE occurs in at least 1 subject,

- 25% or more subjects have GI symptoms of Grade 3 following the first DSMB.

Doses may be adjusted downward at the discretion of the DSMB based on review of safety data including GI adverse events.

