10.2 INTENSITY OF ADVERSE EVENTS

Each AE must be rated on a 3-point scale of increasing intensity according to DMID (Appendix 2):

Note: the semi-colon within the description of the grade indicates ‘or’.

- Grade 1 Mild transient or mild discomfort (<48 hours); no medical intervention/therapy required
- Grade 2 Moderate/mild to moderate limitation in activity—some assistance may be needed; no or minimal medical intervention/therapy required
- Grade 3 Severe/marked limitation in activity, some assistance usually required; medical intervention/therapy required, hospitalizations possible

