A summary table by treatment group will be presented summarizing the intensity (mild, moderate, or severe) associated with each SOC and SOC/PT. A subject will be counted only once for an SOC or an SOC/PT combination. If a subject experiences multiple events in the same SOC or SOC/PT the highest recorded intensity will contribute counts to the summary table.

A summary table, by treatment group, will be presented for the TEAE relationship (reasonable possibility or no reasonable possibility) associated with each SOC and SOC/PT. A subject will be counted only once for an SOC or an SOC/PT combination. If a subject experiences multiple events in the same SOC or SOC/PT the closest relationship to study drug will contribute counts to the summary table.

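### The 25% trigger for an ad hoc DSMB meeting counts moderate GI events without adding 'or higher', so subjects with only severe GI events do not count toward it

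*Protocol*

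**What the plan says.** Protocol 5.6 states that, after the first DSMB review, the board convenes if "the overall relative GI adverse event rate reaches 50% or the rate of moderate GI adverse events reaches 25" per cent. Section 4.1 and the synopsis carry the same condition. None of the three places says whether severe events are included, whether events or subjects are counted, what the denominator is, or what *relative* means.

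Section 10.2 grades every AE on three separate levels: 1 mild, 2 moderate, 3 severe. Section 8.3 has its own severe-event rule: dosing pauses while the DSMB meets if "25% or more subjects have GI symptoms of Grade 3 following the first DSMB". It also pauses for a drug-related SAE in one subject.

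For the final tables, SAP 12.1 counts a subject once per category: "If a subject experiences multiple events in the same SOC or SOC/PT the highest recorded intensity will contribute counts to the summary table". The overall AE summary in the same section also lists any moderate TEAE and any severe TEAE as separate items. Neither statement is about the DSMB trigger. Section 5.6 leaves further detail to a DSMB charter, which is not among the documents.

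**The concern.** A safety trigger should not become harder to meet as outcomes worsen. Here a subject whose single GI event is severe rather than moderate drops out of the 25% count. The Grade 3 rule does not make up for this, because it needs 25% severe by itself. A mixture of the two grades can stay below both limits.

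A mixture is a realistic adverse pattern. In the first challenge cohort, which had no pretreatment, "Moderate to severe cramping, loose stool and/or diarrhea were reported in 6 of the 7 subjects receiving VIS410" (Protocol 1.3). GI toxicity is the known risk of VIS410, and the DSMB may lower doses when it meets. Only two reviews are scheduled, after 30 subjects (Day 5) and 75 subjects (Day 28), in a trial of about 150. At other times a GI-driven meeting depends on these triggers, the pause rules and discretion.

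**Working it through.** The plan gives no count or operating characteristic for these triggers, so there is no stated figure to reproduce.

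**Inputs.** From Protocol 5.6 and 8.3: any-grade GI limit 50%, moderate limit 25%, Grade 3 limit 25%. Assumptions: the any-grade rate is a plain proportion of subjects; arms are pooled; the denominator is 75, for illustration only.

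**Thresholds at 75.** 0.25 × 75 = 18.75, so 25% is reached at 19 (19/75 = 25.3%; 18/75 = 24.0%). 0.50 × 75 = 37.5, so 50% is reached at 38 (37/75 = 49.3%).

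**Direction of the rule, each subject counted once at worst grade.**
- 19 moderate, 0 severe: 25.3% moderate, so the DSMB convenes.
- 18 moderate, 1 severe: 24.0% moderate, 1.3% Grade 3, 25.3% any grade. No trigger is met.

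**Largest untriggered count.** Let M be subjects with moderate but no severe events, S subjects with severe events, L mild-only subjects, and f the share of severe subjects who also have a counted moderate event. Maximise M + S subject to M + ceil(f × S) ≤ 18, S ≤ 18 and M + S + L ≤ 37.

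| f | L | Largest M + S with no GI trigger |
|---|---|---|
| 0 | 0 or 1 | 18 + 18 = 36 (48.0%) |
| 0 | 7 | 18 + 12 = 30 (40.0%) |
| 0 | 13 | 18 + 6 = 24 (32.0%) |
| 0 | 18 | 18 + 1 = 19 (25.3%) |
| 0 | 19 | 18 (24.0%), gap closed |
| 0.5 | 0 | 9 + 18 = 27 (36.0%) |
| 0.75 | 0 | 6 + 16 = 22 (29.3%) |
| 1 | 0 | 18 (24.0%), gap closed |

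With Grade 2 or higher, the constraint becomes M + S ≤ 18 and no gap remains. At f = 0, the untriggered range at other denominators is 13 to 24 of 50, 25 to 48 of 100, and 38 to 74 of 150.

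**How often it would matter.** Multinomial simulation, 100,000 trials, triggers checked after each subject from 31 to 75. All rates are assumed, since the documents give none for this population.

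| Mild / moderate / Grade 3 | f | As written | Grade 2 or higher |
|---|---|---|---|
| 5 / 15 / 15% | 0 | 27% | 94% |
| 5 / 15 / 15% | 0.5 | 64% | 94% |
| 5 / 15 / 15% | 0.75 | 83% | 94% |
| 5 / 15 / 15% | 1 | 94% | 94% |
| 15 / 10 / 5% | 0 | 3% | 14% |
| 17 / 5 / 2% | 0 | 0.2% | 0.3% |

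In the 5/15/15% case, about 76% of trials already meet the Grade 2 or higher limit at subject 31, just after the first review.

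**Adding the SAE pause** to the 5/15/15% case at f = 0. If 5%, 10% or 20% of Grade 3 GI subjects (assumed, independent, any of the 75) have a drug-related SAE, a DSMB meeting is triggered in 57%, 75% or 92% of trials as written, against 96%, 97% or 99% with the revised wording.

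**The case against.** **Worst-grade counting is not in the trigger text.** Section 5.6 speaks of events, whereas 8.3 speaks of subjects. The SAP's separate items for any moderate and any severe TEAE would, on their wording, count a subject with both under both. That is f = 1, where the gap disappears. GI events do cluster: for the 4-hour and 2-hour infusions in VIS410-102, "41 events in 10 subjects vs. 18 events in 6 subjects, respectively" (Protocol 1.3). This stands in part. It makes f = 0 an extreme, but a subject with only a severe event is still left out on any of these counts.

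**The upper end needs no drug-related SAE.** With 18 Grade 3 subjects and an assumed SAE share of 5%, 10% or 20%, the chance of none is 0.95^18 = 40%, 0.90^18 = 15% or 0.80^18 = 2%. This stands, and it makes both 36 of 75 and the 27% figure extremes.

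**The adverse scenario is far from the pretreated data.** If placebo has no GI events, 15% Grade 3 pooled is 15% × 3/2 = 22.5% of VIS410 subjects. In VIS410-102, the loose stool and nausea reported with the diphenhydramine plus ibuprofen or acetylsalicylic acid regimens were mild, apart from one 3800 mg infusion stopped for nausea, vomiting, chills and hot flashes. This also stands, although a trigger exists for the case where expectations fail.

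**The charter may already count moderate or worse.** That is possible. If so, the protocol should say the same.

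A reader might infer that nearly half the subjects could have moderate or severe GI events without the DSMB acting. The documents do not support that. There are scheduled reviews, the SAE pause, DSMB-requested meetings (5.6) and rapid reporting to the sponsor of cramping, diarrhea, nausea and vomiting as AESIs (10.1).

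**Conclusion.** The concern holds as a minor wording defect. On the protocol text, a subject with only severe GI events does not count toward the moderate trigger, and no rule covers the combined moderate-or-worse rate below the 50% any-grade limit.

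The size depends on an undefined counting unit. At 75 subjects the untriggered range runs from 19 up to 36 under worst-grade counting with at most one mild-only subject, and up to 27 with half overlap. It vanishes with full overlap or with 19 or more mild-only subjects. These figures also assume pooled arms, a plain any-grade proportion and no drug-related SAE. The other safeguards limit the consequence but do not correct the trigger. Under a mostly mild profile the two wordings are practically equivalent.

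**What to change.** In Protocol 5.6, 4.1 and the synopsis, and in the charter to match, replace the second trigger with: 25% or more of subjects have a GI adverse event of Grade 2 or higher, each subject counted once at worst grade. Leave the 25% and 50% thresholds as they are. The Grade 3 pause in 8.3 needs no change on the three-point scale of 10.2. The charter should also state the denominator, whether arms are pooled, and what the relative any-grade rate means, because the rewording alone does not settle these.

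Data collection and the SAP are unaffected. The protocol text does need an amendment with ethics approval (12.1), so it is best carried with the next one, and the charter can be clarified at once. The DSMB may convene somewhat more often: from about 3% to 14% of trials by subject 75 under the assumed 15/10/5% rates, and under 0.5% with either wording at 17/5/2%. Convening under this trigger does not stop dosing (5.6).
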